2.3 Study Endpoints

2.3.1 Efficacy Endpoints

The efficacy endpoints for each cohort are outlined in Table 6. Functional outcome measures (e.g., HFMSE/Revised Hammersmith Scale [RHS], 6-minute Walk Test [6MWT], World Health Organization [WHO] Motor Milestones, Revised Upper Limb Module [RULM], 30-Second Sit-to-Stand, Endurance Shuttle Nine Hole Peg Test [ESNHPT], or Endurance Shuttle Box and Block Test [ESBBT]) will be conducted and assessed by the Physical Therapist. Requirements for the order of assessments, duration of assessments and rest periods between assessments will be outlined in a separate Physical Therapist training manual. Similarly, total score from each assessment should there be any missing values will be determined per the instrument tool scoring algorithm for these cases.

Study procedures will not be conducted for patients who develop an AE (e.g., musculoskeletal injury) during the study, irrespective of relatedness to study drug, that the Investigator considers would make it unsafe to perform a functional outcome assessment. Upon resolution of the AE, and if the Investigator assesses it would be safe to do so, performance of that study procedure will be resumed at the next scheduled assessment as indicated in Table 3, Table 4, and Table 5.

Table 6: Efficacy Endpoints by Cohort

	Cohort 1	Cohorts 2 and 3
Primary:	Change from Baseline in the RHS total score at Day 364 (V15)	Change from Baseline in the HFMSE total score at Day 364 (V15)
Secondary:	
 • Change from Baseline in the RHS total score at other prespecified timepoints • Proportion of patients achieving various magnitudes of change in RHS score from Baseline • Change from Baseline in the 6MWT • Change from Baseline in the 30- Second Sit-to-Stand • Change from Baseline in the 10-meter Walk/Run (from the RHS) • Change from Baseline in the time to rise from floor (from the RHS) 	
 • Change from Baseline in the HFMSE total score at other prespecified timepoints • Proportion of patients achieving various magnitudes of change in HFMSE score from Baseline • Change from Baseline in the RULM total score • Proportion of patients achieving various magnitudes of change in RULM from Baseline • Change from Baseline in the number of WHO motor development milestones attained • Proportion of patients who attain a new WHO motor development milestone relative to Baseline


Tertiary:
	
 • Change from Baseline in the Pediatric Evaluation of Disability Inventory Computer Adaptive Test (PEDI-CAT) • Change from Baseline in the Patient-Reported Outcomes Measurement Information System (PROMIS) Fatigue Questionnaire 	
 • Change from Baseline in time to limitation on the ESNHPT or ESBBT • Change from Baseline in the PEDI-CAT • Change from Baseline in the PROMIS Fatigue Questionnaire 
Cohort 3 only:
 
 • Time to therapeutic effect as compared between low- and high-dose SRK-015 [details see section 3.4.3.3]
-------------------------	---	--

[figure not shown]
6MWT = 6-minute Walk Test; ESBBT = Endurance Shuttle Box and Block Test; ESNHPT = Endurance Shuttle Nine Hole Peg Test; HFMSE = Hammersmith Functional Motor Scale Expanded; PEDI-CAT = Pediatric Evaluation of Disability Inventory Computer Adaptive Test; PROMIS = Patient-Reported Outcomes Measurement Information System; RHS = Revised Hammersmith Scale; RULM = Revised Upper Limb Module; WHO = World Health Organization.

2.3.1.1 Revised Hammersmith Scale (RHS)

The RHS will be performed for the ambulatory patient subgroup (Cohort 1). Administration of the RHS includes the timed rise from floor and 10-meter Walk/Run tests. The RHS is a 36-item clinical assessment for physical abilities of patients with Type 2 SMA, and ambulatory and nonambulatory patients with Type 3 SMA. The RHS includes 33 items that are graded on a scale of 0, 1, 2, where 0 denotes the lowest level of ability/function and 2 denotes the highest level of ability (Ramsey 2017). The remaining 3 items are scored 0, 1, where 0 denotes an inability and 1 denotes an ability to achieve. The RHS is calculated by the sum of the 36 items and achievable score range is [0, 69].

The RHS for SMA is based on the original HFMSE. Differences are seen on page 44 of the [RHS manual](#). RHS is used for Cohort 1, as it is appropriate for the SMA Type 3 ambulatory patients. Based on the decline in placebo patients in the HFMSE scale by Day 364 in a previous trial across similar cohort groups to this study (e.g., Darras 2019), any population mean increase above baseline would be clinically relevant for either RHS or HFMSE. Additional analyses will be performed on a patient level with success defined as any patient with a change from Baseline of 3 or more at V15 (Day 364). The figure below is an excerpt from Figure 1 in the RHS manual (SMA REACH UK, 2015):

Figure 4: How the RHS Fits in the Continuum of Outcome Measures in RHS

2.3.1.2 10-meter Walk/Run

The 10-meter Walk/Run test is an enhanced function of the RHS used for ambulant patients with Type 3 SMA. It is a measure of the time taken to walk/run 10 meters.

2.3.1.3 Timed Rise from Floor

The timed rise from floor test is an enhanced function of the RHS used for ambulant patients with Type 3 SMA. It is a measure of the time taken to rise to standing from the floor.

2.3.1.4 6-minute Walk Test (6MWT)

The 6MWT is an assessment of exercise capacity and fatigue that has been used in clinical studies of ambulatory later-onset SMA patients (Young 2016). Ambulant patients in Cohort 1 will complete the 6MWT. Patients are directed to walk along a 25-meter course as fast as possible for 6 minutes. The minute distances and total distance walked over 6 minutes are measured.

2.3.1.5 30-Second Sit-to-Stand

The 30-Second Sit-to-Stand test is used by researchers and clinicians as an assessment of functional lower limb strength (Jones 1999). The test was modified for ambulatory SMA population based on recent research of the modified 30-second Sit-to-Stand being a reliable, feasible tool for use in a general geriatric population with a lower level of function (McAllister 2019) and was related to fall risk in institutionalized veterans (Applebaum 2017, Le Berre 2016). The test measures the maximal number of times the patient can transition from sitting to standing in 30 seconds.

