Type 3 SMA represents approximately 13% of the birth prevalence (Ogino 2004). Patients with Type 3 SMA usually have 3 or 4 copies of the *SMN2* gene. More than 80% of patients with 4 copies of *SMN2* will develop Type 3 SMA (Feldkötter 2002). Milestone achievement can vary greatly in SMA Type 3; some patients may maintain their ability to walk, while other patients have a level of functioning that more closely resembles SMA Type 2 (Finkel 2015). The distinguishing milestone for SMA Type 3 is the ability to walk unaided; however, the majority of patients lose that function over time (Rudnik-Schöneborn 2001). Ambulatory patients with Type 3 SMA commonly suffer from substantial motor functional impairment, as evidenced by abnormal Hammersmith Functional Motor Scale Expanded (HFMSSE) scores and 6-Minute Walk Test (6MWT) distances (Mercuri 2016; Montes 2010). Some patients with Type 3 have orthopedic problems that are comparable to those experienced by patients with SMA Type 2, although generally with later onset and decreased severity (Haaker 2013).

Type 4 SMA is the mildest form of SMA, and its occurrence is rare (<1%). Patients with Type 4 SMA usually have 4 or more copies of the *SMN2* gene. After symptom onset, which has been reported after 10 years of age but more commonly after 20 to 30 years of age (Wang 2007), patients experience mild to moderate muscle weakness and increasing disabilities. Patients are ambulatory, and their life expectancy is normal (Faravelli 2015).

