3.1.7.2 Missing Primary Efficacy Endpoints

For continuous endpoints, where applicable, the last observation carried forward (LOCF) method will be used for missing data, where the patient’s last non-missing value (including baseline) will be used to impute the missing value if a patient is lost to follow-up. For the interim analysis, if there are patients who missed V8 (Day 168) but have V9 (Day 196) or V10 (Day 224) efficacy data, then V9 (Day 196) or V10 (Day 224) data, whichever were obtained earlier, will be used to fill in the gap. For the 12-month analysis, the LOCF method will be used in the descriptive analyses (see Section 3.1.7.3 for intercurrent event handling due to site restriction).

In calculating HFMSE and RHS, if 20% or fewer items are missing, then these items will be imputed to be 0 (unable) when summing all 33 items. If greater than 6 items are missing, then the total score will be set to be missing.

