3.4.1.2 Secondary Efficacy Endpoints

The following secondary endpoints will be analyzed for Cohort 1:

- Change from Baseline in RHS score at prespecified timepoints
- Proportion of patients achieving various magnitudes of change in RHS score from Baseline to scheduled visits. For example, proportion of patients achieving (at least) 5 points, 4 points, 3 points, 2 points or 1 point increase in RHS score from baseline to V15 (Day 364), V8 (Day 168) and all other scheduled visits.
- Change from Baseline in 6MWT to V15 (Day 364), V8 (Day 168) and all other scheduled visits
- Change from Baseline in 30-Second Sit-to-Stand to V15 (Day 364), V8 (Day 168) and all other scheduled visits
- Change from Baseline in 10-meter Walk/Run (from the RHS) to V15 (Day 364), V8 (Day 168) and all other scheduled visits
- Change from Baseline in timed rise from floor (from the RHS) to V15 (Day 364), V8 (Day 168) and all other scheduled visits.

For continuous variables, descriptive statistics (n, mean, standard deviation, median, minimum, maximum) will be provided. The baseline, post-baseline values and changes from baseline will be included, and a 95% CI will be provided for change from Baseline. Mean change from Baseline over time and the corresponding standard errors will be reported graphically.

For categorical variables, frequency tables will be provided to display the number and percentage of patients in each category at each visit.

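### In Cohort 1, change in time on the 10-metre walk/run and the timed rise has no value for a patient who can no longer do the task, so decline is understated

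*Combined protocol and SAP*

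**What the plan says.** **Definition.** Protocol 9.1.1.2 and 9.1.1.3 and SAP 2.3.1.2 and 2.3.1.3 define both tests as elapsed times. For the walk/run: "It is a measure of the time taken to walk/run 10 meters". For the rise: "It is a measure of the time taken to rise to standing from the floor". Neither document gives a value, cap or rank for a patient who cannot do the task, or converts the time to a speed.

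**Analysis.** SAP 3.4.1.2 lists "Change from Baseline in 10-meter Walk/Run (from the RHS) to V15 (Day 364), V8 (Day 168) and all other scheduled visits" and "Change from Baseline in timed rise from floor (from the RHS) to V15 (Day 364), V8 (Day 168) and all other scheduled visits". The method is: "For continuous variables, descriptive statistics (n, mean, standard deviation, median, minimum, maximum) will be provided". It adds Baseline and post-baseline values and a 95% CI for the change.

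**Missing data.** SAP 3.1.7.2 is headed for primary endpoints but worded for continuous endpoints where applicable. It says the patient's "last non-missing value (including baseline) will be used to impute the missing value if a patient is lost to follow-up". The same paragraph then states, without the loss-to-follow-up condition, that the 12-month descriptive analyses use LOCF.

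**Inability on other instruments.** Missing HFMSE and RHS items, up to a limit, count as 0, meaning unable (SAP 3.1.7.2). RULM items that could not be tested also count as 0 (SAP 2.3.1.7). These rules concern total scores only.

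**Entry.** Inclusion criterion 7 (Protocol 7.1) requires ambulatory patients to walk 10 metres unaided at Screening. No criterion requires rising from the floor.

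**The concern.** Losing the task is the worst result a patient can have on a timed test, and it is the one result that a change in time cannot hold. The value is then absent because of the outcome itself, so the patients who remain are a favourable selection. Cohort 1 has a single arm, so no comparator would expose the distortion.

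The situation is foreseeable. Protocol 4.2 says of unaided walking in Type 3 SMA that "the majority of patients lose that function over time". SAP 3.1 also carries the 12-month method into the Extension Periods, where there is more time for losses to occur.

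For the timed rise there is a mirror-image gap. A patient who cannot rise at Baseline and later can has shown a real gain, yet has no Baseline time and so no change score. What is at stake is whether the two reported means and intervals describe the cohort or only those still able to perform.

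**Working it through.** **1. The plan's own figure.** Neither document gives a figure for the timed tests. The only calculation covering Cohort 1 is the paired t-test effect size of 0.66 at n = 20 (Protocol 11.3, SAP 2.2.3). With 19 degrees of freedom and noncentrality 0.66 × √20 = 2.95, power is 0.799, so the stated 80% reproduces. This point does not change it.

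**2. The two readings of SAP 3.1.7.2.** Assume 20 patients, each walking 10 m in 8 s at Baseline (10/8 = 1.25 m/s). By Day 364, k of them have lost the task and the others are unchanged.

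- Dropped: mean change in time is 0 s for any k.
- LOCF, last measured change 0 s: mean change is 0 s.
- LOCF, last measured change +2 s: mean change is k × 2/20 s.
- Speed, unable = 0: mean change is −k × 1.25/20 m/s.

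| k | Dropped | LOCF, last change +2 s | Speed, unable = 0 | % of Baseline speed |
|---|---|---|---|---|
| 1 | 0 s | 0.1 s | −0.06 m/s | −5% |
| 2 | 0 s | 0.2 s | −0.13 m/s | −10% |
| 5 | 0 s | 0.5 s | −0.31 m/s | −25% |

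**3. Range under assumed distributions.** Simulation of 20,000 cohorts of 20. All inputs are assumed: Baseline time lognormal with median 8 s and log-SD 0.6; log ratio of follow-up to Baseline time with SD 0.35; a patient is unable when the time would exceed a cut-off. Entries are mean change in seconds among patients able at Baseline. *All timed* is the change had everyone still been timed. *LOCF* is the case where the last value equals Baseline.

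| Mean log change | Cut-off | Lost per 20 | All timed | Observed only | LOCF |
|---|---|---|---|---|---|
| 0 | 60 s | 0.03 | 0.60 | 0.55 | 0.55 |
| 0 | 20 s | 0.97 | 0.54 | 0.05 | 0.05 |
| 0.10 | 60 s | 0.05 | 1.68 | 1.59 | 1.59 |
| 0.10 | 30 s | 0.57 | 1.61 | 1.17 | 1.14 |
| 0.10 | 20 s | 1.37 | 1.47 | 0.75 | 0.70 |
| 0.20 | 60 s | 0.08 | 2.84 | 2.69 | 2.68 |
| 0.20 | 20 s | 1.91 | 2.51 | 1.48 | 1.33 |

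With mean log change 0.10 (about 10% slowing), observed cases understate by (1.68 − 1.59)/1.68 = 5% at the 60 s cut-off and (1.47 − 0.75)/1.47 = 49% at 20 s. With no mean log change and a 20 s cut-off, nearly all of a small change disappears (0.54 against 0.05 s). LOCF is never better than dropping in these runs.

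**4. A small worked case for the rise.** Assume 12 patients with Baseline times 5, 6, 7, 8, 9, 10, 11, 12, 14, 16, 18 and 20 s. All slow by 5% and the two slowest lose the ability.

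- Dropped: the ten remaining times sum to 98 s, so mean change is 0.05 × 98/10 = +0.49 s.
- LOCF at Baseline: 4.9/12 = +0.41 s, which looks milder still.
- Mean speed, excluding the two: 1/1.05 − 1 = −4.8%.
- Mean speed, scoring them 0: the sum of 1/time goes from 1.2594 to 1.1538/1.05 = 1.0989, or −12.7%.
- If only the slowest patient loses the ability: (1.2594 − 0.05)/1.05 = 1.1518, or −8.5%.

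**The case against.** The strongest reply is that the loss is visible elsewhere and touches nothing decisive. SAP 3.4.1.2 reports n with Baseline and post-baseline values, so a falling n shows and a newly able riser appears among the post-baseline values. SAP 7 lists all data by patient. Both tests are administered within the RHS, whose items go down to 0, so the primary score can register a loss. The 6-minute walk distance and the sit-to-stand count do not share the problem. SAP 3.1.5 plans no formal testing. All of this stands and limits the importance of the point. It does not correct the two means and intervals themselves.

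Handling may also be set out in the physical therapist manual, the RHS manual or the programming specifications, which are not part of these documents. That is possible, but the rule belongs in the SAP.

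A reader might infer four stronger things that the documents do not support:

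- **That affected patients certainly drop out.** This is one reading of SAP 3.1.7.2; the 12-month sentence on LOCF supports the other.
- **That gained ability is lost on both tests.** Everyone in Cohort 1 must walk 10 m at Screening, so this concerns the rise only.
- **That many patients will lose a task within the year.** The Protocol 4.2 statement concerns walking, gives no one-year rate and says nothing about rising.
- **That decline is understated by a fixed factor.** In the 12-patient case, 12.7/4.8 is about 2.7, but with one loss instead of two it is 8.5/4.8, about 1.8. The factor follows from the assumptions.

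Speed is not the only remedy. Ranking unable as worst would also work, and speed gives little weight to a loss in someone already slow.

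**Conclusion.** The point holds as a change that should be made, not as a threat to the trial's main result. Both timed endpoints lack a value for inability, and either reading of the LOCF rule replaces the worst outcome with something better. For the timed rise, gained ability is uncounted as well.

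The size cannot be determined, because the documents give no number of patients unable to rise at Baseline and no rate of losing either task. In the simulated cases with about 10% slowing, the understatement runs from 5% to about half; as a proportion it is larger where true change is near zero. These figures rest on the assumed distributions and on slow patients being the ones who lose the task. If nobody loses or gains a task, there is no effect. Only two descriptive secondary endpoints in one cohort are affected. No primary endpoint, power figure or test changes.

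**What to change.** In SAP 3.4.1.2:

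- Analyse speed: 10/time in m/s for the walk/run and 1/time for the rise. Score 0 when the test was attempted and could not be done, at Baseline as well as later, so that a gained rise counts.
- Keep this separate from tests not done for other reasons, such as the adverse-event provision in SAP 2.3.1. Those remain missing.
- State in SAP 3.1.7.2 whether LOCF reaches secondary endpoints, and that it is not applied to a visit at which the patient was unable.
- Keep change in time as a supportive summary, with its n.
- Tabulate able and unable at Baseline and each visit, with numbers gaining and losing each task.

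The cost is one derived variable per test and one table, from tests already performed. There are two drawbacks: speed of rise is a less familiar unit, and someone must confirm that the database separates unable from not done. If it does not, the RHS item scores may allow the status to be recovered.

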2.3.1.6 Hammersmith Functional Motor Scale Expanded (HFMSE)

The HFMSE assesses the physical abilities of patients with Type 2 and Type 3 SMA (O'Hagen 2007; Glanzman 2011) and will be performed for nonambulatory patient subgroups (Cohorts 2 and 3). It consists of 33 items graded on a scale of 0, 1, 2, where 0 denotes unable, 1 denotes performed with modification or adaption, and 2 denotes without modification or adaptation. The HFMSE total score is the sum of all the 33 items and the maximum score is 66.

In conducting the HFMSE test, Question 3 reported the score for both hands. The higher score will be used in calculating the total score.

2.3.1.7 Revised Upper Limb Module (RULM)

The RULM is a 20-item assessment of upper limb function in nonambulatory SMA patients (young children as well as adults) (Mazzone 2017). The 19 scored items test functions that relate to everyday life, such as bringing hands from lap to table, pressing a button, and picking up a token. The items are scored 0, 1, 2, where 0 denotes unable, 1 denotes able with modification, and 2 denotes able with no difficulty. The RULM is calculated by the sum of the 19 items. The maximum score achievable is 37 (since one item only has possible values of 0 or 1). Responses marked as ‘Could Not Test’ (CNT) will be considered the same as 0 when determining the total score. Non-ambulant patient subgroups (Cohorts 2 and 3) will perform the RULM. The RULM will be completed by patients who are 30 months of age or older at the time of the baseline assessment.

To calculate RULM, where scores for both hands were collected, but only one score is needed, the higher of the two scores will be used to calculate the total score.

2.3.1.8 World Health Organization (WHO) Motor Development Milestones

The WHO Multicentre Growth Reference Study (MGRS) performance criteria are being utilized to assess motor development milestones of patients with Type 2 and nonambulatory Type 3 SMA enrolled in Cohort 2 and Cohort 3. The following table depicts the 6 categories of the milestones (Wijnhoven et al, 2004).

Gross motor milestone	MGRS performance criteria
Sitting without support	Child sits up straight with the head erect for at least 10 seconds. Child does not use arms or hands to balance body or support position
Hands-and-knees crawling	Child alternately moves forward or backward on hands and knees. The stomach does not touch the supporting surface. There are continuous and consecutive movements, at least three in a row
Standing with assistance	Child stands in upright position on both feet, holding onto a stable object (e.g., furniture) with both hands without leaning on it. The body does not touch the stable object, and the legs support most of the body weight. Child thus stands with assistance for at least 10 seconds
Walking with assistance	Child is in upright position with the back straight. Child makes sideways or forward steps by holding onto a stable object (e.g., furniture) with one or both hands. One leg moves forward while the other supports part of the body weight. Child takes at least five steps in this manner

Standing alone	Child stands in upright position on both feet (not on the toes) with the back straight. The legs support 100% of the child’s weight. There is no contact with a person or object. Child stands alone for at least 10 seconds
Walking alone	Child takes at least five steps independently in upright position with the back straight. One leg moves forward while the other supports most of the body weight. There is no contact with a person or object

2.3.1.9 Endurance Shuttle Nine Hole Peg Test (ESNHPT)

The ESNHPT is an endurance test for severely affected patients with SMA. Patients are instructed to repeatedly perform the original 9 Hole Peg Test at 75% of their individual maximum speed. The shuttles refer to the set speed marked by auditory cues, with the test ending when the patient missed 2 consecutive beeps. Primary outcome parameter is ‘time to limitation (Tlim)’, the time a task can be maintained at the preset intensity. Maximum test duration is 20 minutes (Stam 2018). Non-ambulant patients who score ≤ 3 on Item A of the RULM at Screening will perform the ESNHPT at Screening and all subsequent assessments. If a patient maxes out of an endurance test, the PT Advisory Board will be consulted to potentially change assessment designation. The ESNHPT will be completed by patients who are or will turn 8 years of age or older during the study. Patients who turn 8 years of age in Extension Periods A or B who score ≤ 3 on Item A of the RULM at Screening should perform the ESNHPT as early as possible (preferred to begin at E1) and all subsequent visits until the end of the study.

